Protocol Title: Evaluation of Novel Point of Care Coagulation System in Pregnant Women

Study No.: HP-00084317 Principal Investigator: [name] MD, [contact] NCT04301193 Sponsor: Hemosonics LLC

Dated: April 17, 2019

Evaluation of Novel Point of The Care Coagulation System in Pregnant Women

Unexpected obstetric hemorrhage continues to confront anesthesiologists, and obstetric hemorrhage spearheads as the leading cause of maternal mortality and morbidity. One of the hurdles confronting clinicians is the lack of a Point of the care coagulation system that can hasten the clinician management strategy in the right direction. Conventional time-tested coagulation systems take considerable time to obtain results. Thromboelastography (TEG®) and Rotational Throboelastometry (ROTEM®) are welcome additions to assess coagulation quickly. However, these two modalities require expertise and proficient training to perform test, and interpret results. This poses a hurdle for providing coagulation evaluation services around the clock. Therefore, many users of these technologies rely on the conventional laboratory personnel to use these technologies at remote location and thereby delaying expeditious acquisition of results by the clinicians. What is currently required for efficient and effective management of obstetric hemorrhage is a point of care coagulation system in the operating room or labor and delivery suite that is user friendly, easy and quick to perform by any clinician or support staff and does not require certified training. In this study, we evaluate a new point of the care, Quantra Hemostasis Analyzer system to assess coagulation rapidly with ease. The Quantra is a fully automated instrument that requires no sample handling steps from the user. The aim of the present study is to determine how Quantra system performs when compared to conventional coagulation tests at varying level of fibrinogen and clotting factors in the blood obtained from pregnant women.

### Methods:

### Details of the system:

The Quantra is a Point of the Care instrument where all components of test sequence, fluid handling, temperature control, ultrasound transmission, data processing and result output are automated. The device incorporates an embedded processor, a mechanical assembly that provides connection to a peristaltic pump and solenoid valves, heating elements to heat and maintain samples at 37°C, and ultrasound transducers operating in the megahertz range. Figure 1 shows the device used for the study. Quantra uses a plastic cartridge with embedded reagents. The cartridge has 4 test channels that perform 4 parallel and independent measurements using different reagent combinations in each channel. The cartridge has connection mechanism for attaching 3 ml syringe that can contain blood for coagulation analysis.

Channel	Reagents
1	Kaolin, calcium, buffers, and stabilizers
2	Kaolin, heparinase I, calcium, buffers, and stabilizers
3	Thromboplastin, polybrene, calcium, buffers, and stabilizers
4	Thromboplastin, polybrene, abciximab, calcium, buffers, and stabilizers

The reagents used in each channel are shown in the table 1.

The reagents in channel 1 are optimized for the measurements of Clot Time, whereas the channel 2 measures Clot Time without the effect of any potential heparin in the blood sample. Clot Times provides an indication of the functional status of the coagulation factors that lead to fibrin formation.

Furthermore, Clot Time and Heparinase Clot Time (channel 2) can be combined to a clot time ratio for determining the presence of residual heparin in the sample. Channel 3 is optimized to provide measurements of clot stiffness, which combines information about platelets and fibrinogen function. Finally, channel 4 is optimized to measure the Fibrinogen contribution to clot stiffness. Both channels 3 and 4 use hexadimethrine bromide to neutralize residual heparin. The difference between Channel 4 and 1 can provide platelet contribution to clot stiffness.

We designed an in vitro model of obstetric hemodilutional coagulopathy to assess the new technology. We also measured coagulation parameters after reconstituting the dilutional blood with undiluted blood to obtain serial increase in coagulation factors. The results obtained were compared to ROTEM®. The Quantra has been designed to provide results in 20 minutes, the fastest so far among available coagulation technologies.

Quantra uses SEER Sonorheometry. This is a patented technology that uses high-frequency ultrasound pulses to quantify the shear modulus (stiffness) of a blood sample during the process of coagulation. The shear modulus is a parameter that describes the elastic properties of a solid material. The shear modulus of bone tissue is approximately 3.3 hPa, whereas natural rubber is typically approximately 600 Pa.

A focused ultrasound pulse is transmitted into the blood sample to generate a shear wave, causing the sample to resonate once the clot begins to form. As the clot vibrates during resonance, a series of "tracking" ultrasound pulses are transmitted, and the returning echoes are analyzed to estimate the sample's motion. The shape of estimated displacement curve is directly related to the shear modulus of the sample. The time-displacement curve can be compared to theoretic models to determine the actual shear modulus for that specific point in time. Repeated acquisition over time produces a signature curve that shows dynamic changes in shear modulus of the sample during coagulation. From this curve, the start of the clot formation, or clot time, and the stiffness of the clot can be directly estimated. The combination of these two parameters provides information about the functional role of the coagulation factors, fibrinogen, and platelets in the sample. Shear modulus values are determined every 4 seconds by interrogating the blood sample. Clot time, expressed in minutes, is estimated by determining the time at which rate of change in stiffness exceeds a predefined value. Clot stiffness is estimated by identifying the shear modulus value at a specific time point after clot time. This parameter is expressed in units of hectopascals, or hPa (1 hPa= 100 Pa).

### Validation and comparative studies

The validation of the results of Quantra have been performed using a plasma-based control material and Whole blood samples from healthy volunteers (blood samples obtained in 3.2% sodium citrate). Comparative studies were performed against TEG 5000 and the Clauss fibrinogen assay implemented in the StagoSTart4 Hemostasis analyzer (Stago, Asnieres-sur-Seine, France).

### Protocol:

Twenty healthy parturients aged 18-40 years with uncomplicated pregnancies at term gestation, 37 to 41 weeks, presenting for labor, or cesarean delivery will be recruited. Exclusion criteria includes hypertension, preeclampsia, gestational diabetes, preexisting coagulopathy, history of deep vein thrombosis, medications that impair coagulation, or history of pulmonary embolism or thrombosis. Women in active labor receiving intravenous fluids, or oxytocin will be also excluded. After obtaining consent, one table spoon of blood (16.2 ml) will be obtained at the time placement of intravenous cannula along with blood obtained for routine blood work (Hemoglobin and platelet count). The blood will be collected into five citrated Vacutainers (Beckton Dickinson, Franklin Lakes, NJ) each with a maximum capacity of 2.7 mL of blood and containing 0.5 mL 0.109 molar, 3.2% sodium citrated. Citrated blood from each Vacutainer from a single patient will be pooled to eliminate variability in citrate concentration between samples.

#### Protocol Methodology:

Three ml (aliquot 1) of pooled blood will be used analyzed in the Quantra analyzer using 4 channel cartridge for obtaining clot time and clot stiffness. Second aliquot (2) will be used to determine CBC and conventional coagulation tests ( PT, PTT, Fibrinogen, Factor VIII). These three sets (Quantra, CBC, and CL will provide baseline values for Quantra and conventional coagulation tests. 3 ml of pooled blood (aliquot 3) will be spun to yield plasma for additional process (PP).

Six ml (aliquot 4) will be mixed with 18 ml 0.9% normal saline to yield 24 ml of diluted blood (75%). Four ml will be used for Quntra and CL tests. Four additional aliquots of diluted blood sample will be mixed

with pregnant subject's plasma or non-pregnant plasma to yield 15%, and 30% PP aliquots, or 15% and 30% NP aliquots. These diluted blood enriched samples will be analyzed for Quantra and CL tests.

Details of the protocol flow are shown in table 2.

Statistical Analysis:

Results will be presented as Mean±SD for each parameter. Paired t test will be used to study differences in each parameter compared to the baseline for each method.

A scatter plot will be used to compare variations in parameter among three methods of coagulation assessment.

In addition, ANOVA (Analysis of Variance) for multiple comparisons will be used to assess changes in coagulation parameter of each methodology.

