#### **Flow Sheet:**

Collect six blue tops

Run Quantra – One tube (Q1)

Mix 5 tubes = 15 ml

8 ml into four aliquot tubes and spin at 1000 rmp for 10 min.

One aliquot 1 ml for CL (1)

Balance 3.8 ml approx. for PP dilution.

Study protocol

7 ml of blood to 21 ml NS: 28 ml (Sample 2)

75% diluted sample:

3 ml Quantra – Q2

2m to aliquot tube for centrifuge CCL2 and transferred to CL2 (Draw from this CCL2 tube to fresh aliquot tube for CL2)

15% Reconstitution to diluted blood: NP Plasma (Sample 3)

4 ml DB + 0.7 (NP plasma) = 4.7

3ml Quantra Q3

1.7 ml CCL3 centrifuged and transferred to aliquot CL 3

15 % Reconstitution to diluted blood: PP Plasma (Sample 4)

4 ml DB + 0.7 PP =4.7

3ml Quantra Q4

1.7 ml centrifuged in CCL 4 and transferred to aliquot CL 4

30 % Reconstitution to diluted blood:NP Plasma (Sample 5)

4 ml DB + 1.7ml NP =5.7 ml

3 ml Qunatra Q 5

2 ml centrifuged in CCL5 and transferred to aliquot CL 5

30 % Reconstitution to diluted blood:PP Plasma (Sample 6)

4 ml DB + 1.7ml PP =5.7 ml

## 3 ml Qunatra Q 6

# 2 ml centrifuged in CCL 6 and transferred to CL 6

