## FLOW SHEET

Thaw NP Plasma at 37 degree water bath Quantra P1 and CL P1

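### The baseline Quantra sample comes from the pooled blood in the protocol text but from a single unpooled tube in the flow sheet; the tube count and several volumes also disagree

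*Combined protocol and SAP*

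**What the plan says.** The Protocol section states: "The blood will be collected into five citrated Vacutainers". Each tube takes at most 2.7 ml of blood and contains 0.5 ml of citrate, and the total draw is given as 16.2 ml. It then sets a pooling rule and gives its reason: "Citrated blood from each Vacutainer from a single patient will be pooled to eliminate variability in citrate concentration between samples". The Protocol Methodology section applies that rule to the baseline: "Three ml (aliquot 1) of pooled blood will be used analyzed in the Quantra analyzer". A second aliquot of the pool, of unstated volume, serves the CBC and the conventional laboratory tests (labelled CL).

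The Flow Sheet section starts differently: "Collect six blue tops", then "Run Quantra – One tube (Q1", then "Mix 5 tubes = 15 ml". The five-tube mix supplies the baseline laboratory sample (CL1), the subject's own plasma (PP) and the blood that is diluted for samples 2 to 6.

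The Statistical Analysis paragraph compares each parameter with baseline by paired t test, separately for each method.

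**The concern.** One tube plus five mixed tubes makes six, so under the flow sheet Q1 lies outside the pool. An operator who follows the flow sheet breaks the pooling rule in the Protocol section, and the variation between tubes that pooling was meant to remove returns at baseline.

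Two uses of the data are affected:

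- Q1 is the reference for all five Quantra comparisons (Q2 to Q6 against Q1). The laboratory comparisons start from the shared pool, so the two methods are handled unequally in a study whose aim is to compare them.
- Q1 with CL1 is the only undiluted whole-blood pair per subject. The runs in the closing flow sheet ("Thaw NP Plasma at 37 degree water bath Quantra P1 and CL P1") are on non-pregnant plasma and do not replace it. Under the flow sheet, this is the only one of the six pairs whose two members come from different tubes.

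The tube count and several volumes also differ between the sections, so the documents do not fix a single procedure.

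**Working it through.** **Tube count** (Protocol section: five tubes, 2.7 ml each, 16.2 ml drawn; Flow Sheet: six tubes)

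- Five tubes: 5 × 2.7 = 13.5 ml. This does not reproduce 16.2 ml.
- Five tubes with citrate counted as blood: 5 × (2.7 + 0.5) = 16.0 ml. This does not match either.
- Six tubes: 6 × 2.7 = 16.2 ml, which is exact.

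The stated draw therefore agrees with the flow sheet's six tubes, a difference of one tube (2.7 ml).

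**Volumes side by side**

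| Step | Protocol Methodology | Flow Sheet |
|---|---|---|
| Source of Q1 | pool, 3 ml | one tube, before mixing |
| Dilution | 6 + 18 = 24 ml | 7 + 21 = 28 ml |
| Dilution fraction | 18/24 = 75% | 21/28 = 75% |
| Sample 2 testing | 4 ml | 3 + 2 = 5 ml |
| Blood spun | 3 ml, PP only | 8 ml, PP and CL1 |
| Baseline CBC | from the pool | no step; 8 + 7 = 15 ml uses the whole pool |

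The dilution fraction is the same in both. The flow sheet's reconstitution volumes also agree with their labels: 0.7/4.7 = 14.9% and 1.7/5.7 = 29.8%.

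The spin volumes are not interchangeable. The flow sheet needs 0.7 + 1.7 = 2.4 ml of PP plasma. Its implied yield is (1 + 3.8)/8 = 60%. At that yield a 3 ml spin gives 3 × 0.60 = 1.8 ml, and reaching 2.4 ml would need a yield of 2.4/3 = 80%.

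**Share of pairs affected**

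6 samples × 20 subjects = 120 Quantra-laboratory pairs. The Q1-CL1 pairs number 20, and 20/120 = 17%. The plasma-only runs are left out because their number is not stated.

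**Size of the specimen difference**

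Let s be the SD between tubes of one draw, with independent tube errors. The documents give no value for s.

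- Per subject: SD(Q1 tube − five-tube pool) = s × √(1 + 1/5) = 1.095s.
- On the mean of 20 subjects: 1.095s/√20 = 0.245s.

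| Assumed s (% of reading) | Per subject | On the mean of 20 |
|---|---|---|
| 2 | 2.19% | 0.49% |
| 5 | 5.48% | 1.22% |
| 10 | 10.95% | 2.45% |

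With a common pool the specimen difference before dilution is zero.

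**The case against.** The strongest reply is that the consequence is slight. All tubes come from one subject and one collection, and pooling still covers CL1 and samples 2 to 6, so most of its purpose is met. No tube-to-tube SD is documented, and the 2 to 10% values have no anchor in the text. The 17% figure belongs to no planned analysis. All of this stands, and it is why the point is rated minor.

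The tube count can be partly explained: five may be the number of tubes pooled, with the sixth used for Q1. That would make the count a wording slip, but it would not account for a baseline Quantra aliquot taken from the pool.

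The Protocol Methodology section refers to a table 2 for the flow. No table with that label appears in the available text. It may be the flow sheet, with the text a summary, or it may have been lost in extraction. Even if it is the flow sheet, the two sections still disagree on where Q1 comes from. Running Q1 straight from one tube could be deliberate, but no reason is given and it contradicts the stated rule.

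The missing CBC step is only a query. The Protocol section mentions a draw taken "along with blood obtained for routine blood work (Hemoglobin and platelet count", which may cover part of it. Full tubes would also give 5 × 3.2 = 16.0 ml, leaving 1 ml beyond the flow sheet's 15 ml.

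The different dilution volumes do not matter for the dilution itself, since both give 75%.

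**Conclusion.** The concern holds, at minor severity. The conflict over the baseline Quantra sample is a contradiction in the text and does not depend on any assumption. The mismatch between five tubes and 16.2 ml is plain arithmetic.

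The size of the effect is conditional: 1.10s per subject and 0.245s on the 20-subject mean, assuming independent tube errors and an undocumented s. The effect is more likely added noise than a consistent shift, and it is small against a 75% dilution. No conclusion of the study is shown to change.

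**What to change.** In the Protocol section, state six tubes to match the 16.2 ml already given. In the Protocol Methodology and Flow Sheet sections, pool all six before any aliquot is taken, draw both Q1 and CL1 from that pool, and use one set of volumes. Name the source of the baseline CBC (pool or routine blood work) and identify the table that the text refers to.

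One set of volumes that works, as an example only, at the flow sheet's 15/5 = 3.0 ml per tube:

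- **Pool:** 3 (Q1) + 7 (spin for CL1 and PP) + 6 (dilution) + 1 (CBC, assumed volume) = 17 of 18 ml. It holds down to 17/6 = 2.83 ml per tube. Full tubes would give 6 × 3.2 = 19.2 ml.
- **Plasma:** 7 × 0.60 = 4.2 ml against 0.7 + 1.7 + 1 = 3.4 ml needed, sufficient at any yield of 3.4/7 = 49% or more. The 60% rests on one approximate figure in the flow sheet.
- **Diluted blood:** 6 + 18 = 24 ml against 3 + 2 + 4 × 4 = 21 ml used.

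The cost is protocol wording, with no blood beyond the stated 16.2 ml and no extra runs. Compared with the flow sheet, spare diluted blood falls from 28 − 21 = 7 ml to 24 − 21 = 3 ml. Spare PP plasma falls from 3.8 − 2.4 = 1.4 ml to 4.2 − 3.4 = 0.8 ml. Q1 has to wait until the tubes are mixed.

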#### CL P and Q P

Will be the IDs NP plasma

We will see if one bag will suffice into 20 aliquots, or multiple bags needed.

Our lab is able to provide the plasma

All set with approval for this.

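### The aim is to compare Quantra with conventional tests, but the only planned cross-method output is a scatter plot, so the plan gives no estimate of how well Quantra tracks them

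*Combined protocol and SAP*

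**What the plan says.** The opening section gives a between-method aim: to determine "how Quantra system performs when compared to conventional coagulation tests at varying level of fibrinogen and clotting factors".

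The Statistical Analysis text under Protocol Methodology lists four outputs:

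- Mean±SD for each parameter.
- A comparison with baseline: "Paired t test will be used to study differences in each parameter compared to the baseline for each method".
- A plot: "A scatter plot will be used to compare variations in parameter among three methods of coagulation assessment".
- A multi-level comparison: "ANOVA (Analysis of Variance) for multiple comparisons will be used to assess changes in coagulation parameter of each methodology".

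The three methods are not named there. Details of the system says "The results obtained were compared to ROTEM". Protocol Methodology, describing the baseline aliquots, says "These three sets (Quantra, CBC, and CL will provide baseline values for Quantra and conventional coagulation tests". The Flow Sheet lists Quantra runs Q1 to Q6 and laboratory samples CL 1 to CL 6 for each woman.

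**The concern.** A comparison of methods needs at least one quantity computed from the two methods' values on the same sample. Here the only such output is a picture. Two studies could follow this plan to the letter, one in which Quantra reflects a woman's fibrinogen and one in which it does not, and both could report the same set of within-method changes after dilution.

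The design makes a picture especially weak evidence. Saline dilution and plasma addition push Quantra and the laboratory tests in the same direction in every woman. A plot that pools the six sample types will show a strong trend from those steps alone, and a reader may credit it to Quantra as information about individual women.

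**Working it through.** **1. Sorting the planned outputs.** The documents give no sample-size, power or precision figure for this comparison, so there is nothing of the plan's own to reproduce.

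| Output | Uses Quantra and laboratory values of one sample together? | Gives an estimate? |
|---|---|---|
| Mean±SD | No | Within method only |
| Paired t test against baseline | No | Within method only |
| ANOVA | No | Within method only |
| Scatter plot | Yes | No |

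No correlation, regression, agreement measure or confidence interval appears anywhere else. The section on validation and comparative studies describes earlier work.

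**2. The three methods.** ROTEM is named in Details of the system, but neither Protocol Methodology nor the Flow Sheet contains a ROTEM run. If the three are Quantra, CBC and conventional laboratory tests (CL), CBC is named only for the baseline aliquot. On the listed flow, samples 2 to 6 have Quantra and CL values only.

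**3. Factor levels created by the design.** The volumes come from the Flow Sheet: 7 ml blood plus 21 ml saline, then 4 ml of diluted blood plus 0.7 or 1.7 ml plasma (for example "4 ml DB + 0.7 (NP plasma) = 4.7"). Haematocrit of 35% is an assumption.

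- Plasma in 7 ml blood: 7 × 0.65 = 4.55 ml. After saline: 4.55 / (4.55 + 21) = 0.18.
- 4 ml of diluted blood holds 4 × 4.55/28 = 0.65 ml plasma in 4 × 25.55/28 = 3.65 ml of cell-free fluid.
- Plus 0.7 ml plasma: (0.65 + 0.7) / (3.65 + 0.7) = 0.31.
- Plus 1.7 ml plasma: (0.65 + 1.7) / (3.65 + 1.7) = 0.44.

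Samples 1 to 6 therefore sit at 100, 18, 31, 31, 44 and 44% of baseline. Haematocrit of 30 to 40% changes these only to 17–19, 30–32 and 43–44%.

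**4. What a pooled plot shows when the assays share nothing between women.** Assumptions: each assay is proportional to factor level L, added plasma carries the woman's own factor level, the between-woman CV is c, and the noise CV is c/2. Then

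pooled r ≈ Var(L) / [Var(L) + E(L²) × 1.25c²], with Var(L) = 0.0693 and E(L²) = 0.2684.

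| c | Formula | Simulated (20 women × 6 samples, 4,000 data sets) |
|---|---|---|
| 15% | 0.90 | 0.91 |
| 20% | 0.84 | 0.84 |
| 25% | 0.77 | 0.78 |
| 30% | 0.70 | 0.71 |

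The simulated correlation within a sample type is 0.00 throughout. Variants across c = 15 to 30%:

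- Without the baseline sample: 0.74 to 0.42.
- Noise CV equal to c: 0.86 to 0.59.
- Non-pregnant (NP) plasma from one shared donor, at 100% or 60% of the pregnant mean: 0.92 to 0.73–0.75.
- Repeated-measures correlation: 0.96 to 0.86.

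**5. The same plot when both assays measure the same factor.** Pooled r rises only to 0.98 to 0.93. The correlation within a sample type moves from 0.00 to about 0.79 in samples 1, 2, 4 and 6, close to the theoretical 1/1.25 = 0.80. The within-type result separates the two cases clearly; the pooled one barely does.

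Samples 3 and 5 carry NP plasma, and whether one bag will serve all women is still open ("We will see if one bag will suffice into 20 aliquots, or multiple bags needed"). With shared donor plasma at 100%, the woman's own factor is 0.65/1.35 = 48% of the total in sample 3 and 0.65/2.35 = 28% in sample 5. Even perfectly related assays would correlate only 0.46–0.59 and 0.22–0.37 there (donor at 100% to 60%).

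**6. Precision with 20 women.** The 95% CI is tanh[atanh(r) ± 1.96/√(20 − 3)]. At r = 0.8 it runs from 0.55 to 0.92; at r = 0.5, from 0.07 to 0.77. Treating all 120 pairs as independent would give 0.72 to 0.86 at r = 0.8, which is too narrow because there are six pairs per woman.

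**7. Choice of scale and model** (simulated, 800 to 1,000 data sets per setting). For a random-intercept slope, the 95% CI covered the mean slope in 66–70% of runs on raw values and 94–98% on log values. With sample type added, the false-positive rate at nominal 5% was 35–39% on raw values, 12–17% on log values of all six types with shared NP plasma, and 6.5% on log values of samples 1, 2, 4 and 6. In that last model the slope averages 0.61–0.64 when the true value is 1. Within-type Fisher tests rejected in 5–7% of null runs.

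**The case against.** The strongest reply is that the design is being recast as a flaw. The aim speaks of performance at varying factor levels, the protocol creates those levels by dilution and plasma addition, and both assays moving together is the intended signal. No section asks for a between-woman correlation. The plan also never proposes a pooled correlation, so the simulation sizes a statistic the plan does not contain. This is a 20-woman in vitro study, and the paired values are kept, so an estimate can be computed later.

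Much of this is fair. Tracking the induced range belongs to the aim, but the plan gives no estimate of that either. The simulation shows why a plot, or the pooled correlation someone might add to it, would mislead; it does not measure the missing estimate. It has no platelet term, so it suits the fibrinogen channel at best, and clot time against PT or PTT was not modelled. Because data are retained, the loss is pre-specification.

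A second reply is that the slope across the range is also high when the assays are unrelated between women. That stands. It is why the slope must be labelled as including dilution and reported beside the within-type correlations. Three pairs by six sample types make 18 correlations at n = 20, so they should be read as estimates with intervals and not as 18 tests.

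**Conclusion.** The concern holds. Of four planned outputs, one crosses methods and none estimates how Quantra relates to the conventional tests. This rests on the text alone. The undefined three methods, and a ROTEM comparison with no ROTEM run in the listed flow, mean the plot itself cannot be drawn as described.

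The risk of misreading is large under the stated assumptions: a pooled correlation of 0.91 to 0.71 with no between-woman relation, against 0.98 to 0.93 with a full one. These figures depend on assumed haematocrit, CVs, noise and proportional assays, none of which the documents give. The conclusion that an estimate is missing does not. The point should be fixed: the study can be completed as planned without answering its own question, and the remedy is cheap.

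**What to change.** 1. State which three methods are meant, and reconcile the ROTEM sentence in Details of the system with the sample flow.
2. Pre-specify the pairs: fibrinogen contribution to clot stiffness against laboratory fibrinogen; clot time against PTT; clot time against PT.
3. For each pair report two results:
   - *Tracking across the induced range*: slope from a mixed model on log values, with a random intercept per woman and a 95% CI, labelled as including the dilution effect.
   - *Association beyond dilution*: correlation within each sample type with a Fisher 95% CI. Lead with own-plasma samples 1, 2, 4 and 6, and mark samples 3 and 5 as restricted range.
4. As a check, refit the mixed model with sample type as a fixed effect on log values of samples 1, 2, 4 and 6. Read it for direction only, since its slope is biased towards zero.
5. Do not rely on repeated-measures correlation alone.
6. Keep the scatter plot, coloured by sample type, as illustration.

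The cost is a rewritten statistical paragraph and a few lines of code, with no new blood or patients. The downside is slightly more analysis and wide within-type intervals.
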